8.1.2 Interim Monitoring Visits (IMVs)

Interim Monitoring Visits will be conducted to confirm participants' rights are being protected; the study is being conducted according to the protocol and applicable regulations; and to confirm accurate reporting of participant safety data and study endpoints.

8.1.3 Close-Out Visit (COV)

A Close-Out Visit will be conducted to ensure that all study data and other study documentation is complete and accurate and that all study records have been reconciled.

8.2 TRAINING OF STAFF

The Investigator or designee will ensure that appropriate training relevant to the study is provided to all staff involved in the study, and that any new information relevant to the performance of this study is forwarded in a timely manner to the staff.

8.3 AUDITS AND INSPECTIONS

Good Clinical Practice regulations require independent inspections of clinical program activities. Such inspections may be performed at any time before, during, and after the study.

Authorized representatives of the Sponsor, regulatory agencies and/or an IRB may perform audits or inspections, including source data verification. The purpose of an audit or inspection is to systematically and independently examine all study-related activities and documents to determine whether these activities were conducted, and data were recorded, analyzed and accurately reported, according to the protocol, ICH/GCP guidelines and any applicable regulatory requirements. The Investigator or designee will contact the Sponsor immediately if contacted by a regulatory agency about an inspection at their site.

The Investigator and study staff are responsible for maintaining a comprehensive and accurate filing system of all study-related documentation that will be suitable for inspection at any time by the Sponsor, its authorized representative, and other regulatory agencies.

9 ADVERSE EVENTS

9.1 DEFINITIONS

9.1.1 Adverse Event (AE)

An AE is defined as any untoward medical occurrence in a patient or clinical trial participant administered a medicinal product and which does not necessarily have a causal relationship with this treatment. The AEs would not include information recorded as medical history at screening for preplanned procedures for which the underlying condition was known and no worsening occurred. An adverse reaction is any untoward and unintended response to an IMP-related to any dose administered.

A suspected adverse reaction is any AE for which there is a reasonable possibility that the IMP caused the AE. For the purpose of Investigational New Drug (IND) safety reporting, "reasonable possibility"

means there is evidence to suggest a causal relationship between the IMP and the AE. Suspected adverse reaction implies a lesser degree of certainty about causality.

Any increase in the severity and/or the frequency of a concomitant disease is considered an AE.

9.1.2 Serious Adverse Event (SAE)

A Serious Adverse Event is any adverse event that results in any of the following outcomes:

- Death
- Life-threatening; ie, the participant was, in the opinion of the investigator, at immediate risk of death from the event as it occurred. It does not include an event that, had it occurred in a more severe form, might have caused death.
- Persistent or significant incapacity/disability or substantial disruption of the ability to conduct normal life functions.
- Requires in-patient hospitalization or prolongs hospitalization.
 - Hospitalization itself should not be reported as an SAE; whenever possible the reason for the hospitalization should be reported.
 - Hospitalizations or prolonged hospitalizations for social admissions (ie, those required for reasons of convenience or other non-medical need) are not considered SAEs.
- Congenital anomaly/birth defect.
- Other medically significant events that, based upon appropriate medical judgment, may jeopardize the participant and may require medical or surgical intervention to prevent one of the outcomes listed above; eg, allergic bronchospasm requiring intensive treatment in an emergency room or home, blood dyscrasias or convulsions that do not result in hospitalization, or the development of drug dependency or drug abuse.

9.1.3 Nonserious Adverse Event

Adverse events are all AEs that do not meet the criteria for a "serious" AE.

9.1.4 Immediately Reportable Event (IRE)

The following events will be reported immediately to the Sponsor.

- Any SAE.
- Any AE of special interest (AESI).
- Any AE related to occupational exposure.
- Potential serious hepatotoxicity.
- Confirmed pregnancy.

9.1.5 Psychiatric Adverse Events

The investigator (or designee) will review participant responses to the C-SSRS. The C-SSRS will be used to screen for suicidal ideation within the last 12 months and suicidal behavior within the last 24 months from screening. Potential participants who score >0 on the screening C-SSRS for suicidal ideations (answer "Yes" to questions 1-5 in the *SUICIDAL IDEATION* section) or a score >0 for Suicidal Behavior (answer "Yes" to any questions in the *SUICIDAL BEHAVIOR* section) at screening (Visit 1) or at Baseline (Visit 2) will be excluded from study participation, and, at the discretion of the study physician/physician assistant, referred to appropriate psychiatric treatment. The C-SSRS will be administered by trained clinical research staff at every visit, including the screening visit (V1 through V6). The "Screening" version will be administered at V1, and the "Since Last Visit" version will be administered at V2 through

V6, inclusive. Any changes in the scoring will be evaluated by licensed medical professionals, with recommendations for referral to appropriate medical care provided to the participant when required, at the discretion of the study physician/physician assistant.

9.1.6 Changes in Clinical Laboratory Test Values

It is the investigator's (or designee's) responsibility to review the results of all laboratory tests as they become available. This review will be documented by the investigator's dated signature on the laboratory report. For each abnormal laboratory test result, the investigator needs to ascertain if this is an abnormal (ie, clinically significant) change from baseline for that individual participant. This determination, however, does not necessarily need to be made the first time an abnormal value is observed. The investigator may repeat the laboratory test or request additional tests to verify the results of the original laboratory tests. If this laboratory value is considered medically relevant by the investigator (participant is symptomatic, requiring corrective treatment or further evaluation), or if the laboratory value leads to discontinuation, and/or fulfills a seriousness criterion, this is considered an AE.

9.2 COLLECTION OF SAFETY EVENTS FROM PARTICIPANTS

The investigator will periodically assess participants for the occurrence of AEs. To avoid bias in eliciting AEs, participants should be asked the non-leading question: "How have you felt since your last visit?" All AEs (serious and nonserious) reported by the participant must be recorded on the source documents and eCRF. Serious AE collection is to begin after a participant has signed the eICF.

Use medical terminology in AE reporting. Adverse events should be reported as a single unifying diagnosis whenever possible or, in the absence of a unifying diagnosis, as individual signs or symptoms. Exacerbation or disease progression should be reported as an AE only if there are unusual or severe clinical features that were not present, or experienced earlier, or not expected based on the course of the condition.

Information recorded when collecting AEs will include: thorough description of the AE, seriousness assessment, start and stop dates (if known), circumstances leading up to the event, clinical elements such as clinical course, specific vital signs and test results that may explain the pathophysiology of the event, as well as alternative explanations to its occurrence, the action taken with the investigation product/procedures due to the AE, the participant's disposition in the study after the occurrence of the AE and the final outcome of the AE (if known).

Any exacerbation/worsening or increased frequency of an AE or pre-existing condition shall be evaluated and recorded.

9.2.1 Period of Collection

All existing health conditions identified during the Screening Period will be recorded as concomitant disease and the participant's eligibility will be reviewed. Any AEs which occur during the screening session will be captured by the study site staff and assessed by the Investigator or designee in order to establish relationship or relatedness in respect to study procedures.

Any new, clinically relevant, abnormal finding detected during the study or worsening of a pre-existing condition/concomitant disease will be documented as an AE or an SAE.

All ongoing AEs at the End of Study participation will be followed-up by the Investigator or designee until they have improved, resolved, stabilized (i.e., no worsening of condition), or until an acceptable explanation has been found. The Investigator or designee will refer the participant to their Primary Care Provider for follow up of those AE when appropriate.

9.3 ASSESSMENT OF ADVERSE EVENTS

9.3.1 Severity of Adverse Events

For each AE/SAE, the intensity will be graded on a 3-point intensity scale:

- Mild: The AE is easily tolerated and does not interfere with daily activity.
- Moderate: The AE interferes with daily activity, but the participant is still able to function.
- Severe: The AE is incapacitating and requires medical intervention.

9.3.2 IMP Causality

In general, all AEs and SAEs will be assessed by the Investigator or designee as either 'related' or 'not related'.

- Not related: The temporal relationship of the clinical event to study procedures and/or the study medication makes a causal relationship unlikely, or, concomitant medication, therapeutic interventions, or underlying conditions provide a sufficient explanation for the observed event.
- Related: The temporal relationship of the clinical event to study procedures and/or the study medication makes a causal relationship possible, and concomitant medication, therapeutic interventions, or underlying conditions do not provide a sufficient explanation for the observed event.

[figure not shown]

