7.3.3 Blood Draw

The risks associated with venipuncture are minimal and include momentary discomfort and/or bruising. Infection, excess bleeding, clotting, and fainting are also possible, although unlikely.

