9.2 Adverse Events

All AEs are coded using Medical Dictionary for Regulatory Activities (MedDRA). A TEAE is defined as an AE which starts after start of first IMP or an AE continues from

Protocol 405-201-00055 Statistical Analysis Plan

baseline of the specific corresponding duration and was serious, trial drug-related or results in death, discontinuation, interruption or reduction of IMP.

The incidences of the following TEAEs will be reported:

- TEAEs
- TEAEs by severity
- Potentially drug-related TEAEs
- TEAEs with an outcome of death
- Serious TEAEs
- Discontinuations due to TEAEs
- Treatment-emergent adverse events of special interest (AESI) related to **CCI**
[REDACTED]
- TEAEs related to Abuse-Potential

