CT-8.2.3 Incidence of Treatment-emergent Adverse Events Greater Than or Equal to 2% by System Organ Class and MedDRA Preferred Term (Safety Analysis Set)

CT-8.2.4 Incidence and Occurrence (Number of Events) of Potentially Drug-Related Serious TEAEs by System Organ Class and MedDRA Preferred Term (Safety Analysis Set)

CT-8.2.5 Incidence and Occurrence (Number of Events) of Serious TEAEs by System Organ Class and MedDRA Preferred Term (Safety Analysis Set)

CT-8.2.6 Incidence and Occurrence (Number of Events) of Non-Serious TEAEs by System Organ Class and MedDRA Preferred Term (Safety Analysis Set)

CT-8.3.1 Incidence of Potentially Drug-related Treatment-emergent Adverse Events by System Organ Class and MedDRA Preferred Term (Safety Analysis Set)

CT-8.3.2 Incidence of Potentially Drug-related Treatment-emergent Adverse Events by System Organ Class, MedDRA Preferred Term and Severity (Safety Analysis Set)

CT-8.4.1 Incidence of Deaths Due to Treatment-emergent Adverse Events by System Organ Class and MedDRA Preferred Term (Safety Analysis Set)

CT-8.4.2 Incidence of Deaths Due to Treatment-emergent Adverse Events by System Organ Class and MedDRA Preferred Term and Severity (Safety Analysis Set)

CT-8.5.1 Incidence of Serious Treatment-emergent Adverse Events by System Organ Class and MedDRA Preferred Term (Safety Analysis Set)

CT-8.5.2 Incidence of Serious Treatment-emergent Adverse Events by System Organ Class, MedDRA Preferred Term and Severity (Safety Analysis Set)

Protocol 405-201-00055 Statistical Analysis Plan

CT-8.6.1 Incidence of Treatment-emergent Adverse Events Resulting in Discontinuations of Trial Medication by System Organ Class and MedDRA Preferred Term (Safety Analysis Set)

CT-8.6.2 Incidence of Treatment-emergent Adverse Events Resulting in Discontinuations of Trial Medication by System Organ Class, MedDRA Preferred Term and Severity (Safety Analysis Set)

CT-8.7.1 Incidence of Treatment-emergent Adverse Events of Special Interests by System Organ Class and MedDRA Preferred Term (Safety Analysis Set)

CT-8.7.2 Incidence of Treatment-emergent Adverse Events of Special Interests by System Organ Class and MedDRA Preferred Term and Severity (Safety Analysis Set)

CT-8.8.1 Incidence of Treatment-emergent Adverse Events related to Abuse-Potential by System Organ Class and MedDRA Preferred Term (Safety Analysis Set)

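### Protocol 9.3.2 pools procedure and drug causality in one rating, so procedural events can enter the SAP's potentially drug-related TEAE tables

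*Protocol*

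**What the plan says.** Protocol 9.3.2 (IMP Causality) asks the investigator or a designee for one binary judgement per AE or SAE. The two categories are defined as follows:

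- "Related: The temporal relationship of the clinical event to study procedures and/or the study medication makes a causal relationship possible", provided that concomitant medication, therapeutic interventions or underlying conditions do not explain the event.
- "Not related: The temporal relationship of the clinical event to study procedures and/or the study medication makes a causal relationship unlikely", or one of those other factors explains it.

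No separate rating for study procedures is described. Two other protocol sections keep drug and procedure apart. Section 9.1.1 looks at the drug alone: "A suspected adverse reaction is any AE for which there is a reasonable possibility that the IMP caused the AE". Section 9.2.1 looks at procedures alone: AEs in the screening session are "assessed by the Investigator or designee in order to establish relationship or relatedness in respect to study procedures".

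The SAP states in section 1 that it is consistent with protocol version 3.0, and in section 14 that there are no changes to the planned analyses. Its section 9.2 lists "Potentially drug-related TEAEs" among the outputs, and section 17 gives the tables: CT-8.2.4 (serious), CT-8.3.1, and CT-8.3.2 (by severity). The SAP does not say which field makes an event potentially drug-related. The TEAE definition in SAP 9.2 has two limbs: events starting after the first IMP dose, and events continuing from baseline that meet one of several conditions, one of which is being trial drug-related.

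**The concern.** The rating is labelled as drug causality, but its wording lets an event caused only by a study procedure be called related. The protocol expects such events. Section 7.3.3 says of blood draws: "The risks associated with venipuncture are minimal and include momentary discomfort and/or bruising". It also lists infection, bleeding, clotting and fainting as possible though unlikely.

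The trial is single-group and open-label, so no concurrent arm shows the background rate of procedural events. Investigator relatedness is the only drug attribution in the planned AE tables. If procedural events are counted as related, the potentially drug-related incidence is overstated, and nothing elsewhere in the plan would correct it.

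**Working it through.** No drug-related rate is stated in the documents, so there is no figure to reproduce. The check is mainly a reading of the text.

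**Step 1: apply both definitions to a bruise from the V4 draw.** A causal link to the procedure is possible, which satisfies the related category through its procedure part. A causal link to the medication is unlikely, which satisfies the not-related category through its medication part. The listed alternative explanations do not clearly break the tie: a research blood draw is not concomitant medication or an underlying condition, and is not obviously a therapeutic intervention. Both answers are open, and the result depends on how each assessor reads the sentence.

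**Step 2: follow a related rating into the SAP.** Protocol 6.5.1 and 6.5.2 place safety blood draws at V1 (before dosing), V4 and V6. Events from V4 or V6 start after the first dose, so they are TEAEs under the first limb. If rated related, nothing in the SAP keeps them out of CT-8.3.1 and CT-8.3.2, or out of CT-8.2.4 if they are serious.

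**Step 3: the screening draw.** An event from V1 starts before the first dose. It becomes a TEAE by this route only if it persists to the first dose and someone reads the pooled rating as trial drug-related. This is a minor route.

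**Step 4: what does not depend on the rating.** The abstinence endpoint (SAP 8.1.1) uses self-report and CO. The nausea endpoint (SAP 8.2.1) counts any nausea TEAE whatever its cause. CT-8.1 and CT-8.2.1 are not split by causality; only the minor route in Step 3 could add an event to CT-8.2.1.

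**Step 5: size.** The denominator is the Safety Analysis Set, taken as 50 (SAP 3.3) if all enrolled participants are dosed. Each participant whose only related TEAE is procedural adds 1/50 = 2.0 percentage points. With no dropout there are 50 × 2 = 100 on-treatment draw visits.

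A total would need inputs that the documents do not give. To show how much it depends on them, let p be an assumed probability of a recorded procedural AE per draw visit, and b an assumed share of participants already counted as drug-related. Assume also that visits are independent of each other and of b, and that every such event is rated related. Then

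points added = 100 × (1 − b) × [1 − (1 − p)²]

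| p (assumed) | 1 − (1 − p)² | b = 60% | b = 20% |
|---|---|---|---|
| 1% | 0.0199 | 0.8 | 1.6 |
| 5% | 0.0975 | 3.9 | 7.8 |
| 10% | 0.19 | 7.6 | 15.2 |

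The spread from 0.8 to 15.2 points comes entirely from the assumptions. It is not an estimate for this trial.

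**The case against.** The strongest reply is that this is loose drafting with little consequence. The section heading points to the IMP, and the not-related wording lets an assessor rate a draw-site bruise as not related. The eCRF is not among the documents, so a separate IMP field cannot be ruled out. Protocol 9.2 collects the circumstances of each AE and alternative explanations, and 9.9 lets the sponsor ask for more information on causality, so a blood-draw event could be recognised. The drug-related tables are broken down by preferred term, where a draw-site event would show on its own line. No hypothesis, threshold or stopping rule uses the drug-related rate.

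Much of this stands, and it rules out several stronger readings that a reader might infer:

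- That procedural events must be rated related. They fit both categories.
- That the SAP demonstrably uses the pooled rating. It names no source field.
- That a screening bruise would become a TEAE. Section 9.2.1 treats screening-session events as a procedure question, and nothing tells a programmer to map procedure-related to drug-related.
- That 9.1.1 contradicts 9.3.2. It defines a different term, the suspected adverse reaction, and does not rely on the 9.3.2 rating.
- That the inflation has a known size, such as 5 to 10 points. No event probability is given, and 7.3.3 calls the risks of venipuncture minimal.

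The core remains. The pooled rating is the only causality rating described that could feed these tables, and a rating that permits opposite answers for the same event is itself a defect. Narrative detail in the AE record is not a second rating, and the SAP has no rule for using it. The breakdown by term helps with a bruise but less with a faint, because 7.3.1 lists dizziness and a heart rate increase on standing among the drug's reported effects.

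**Conclusion.** The concern holds as a matter of what the plan permits. Procedural events on or after the first dose can be rated related, can enter CT-8.3.1 and CT-8.3.2 (and CT-8.2.4 if serious), and may inflate the potentially drug-related TEAE rate. Each procedural event counted this way can move that rate only upward, by 2 points per participant with no other related TEAE, assuming 50 dosed.

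The documents do not show that this will happen or how often. The conclusion assumes that the described rating feeds the tables and that some assessors read it through its procedure part. The effect is confined to drug attribution in the safety tables, so the point is a worthwhile correction and not a threat to the trial's main results.

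**What to change.** In Protocol 9.3.2 and the eCRF, replace the pooled rating with two yes/no fields per AE: related to IMP, and related to a study procedure. Word each category against one cause only, so that the two answers to each question exclude each other.

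In SAP 9.2, define potentially drug-related, and the trial drug-related condition in the second TEAE limb, from the IMP field only. That matches the IMP-only wording of Protocol 9.1.1 and keeps the procedure question raised in 9.2.1 in its own field.

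The cost is one extra eCRF field and short edits to the two documents. No visits or assessments are added.

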9.4 IMMEDIATELY REPORTABLE EVENTS

The investigator must immediately report after either the investigator or site personnel become aware of any SAE, AE related to occupational exposure, AESI, potential serious hepatotoxicity, or confirmed pregnancy, by telephone, fax, or e-mail to the sponsor using the contact information on the cover page of this protocol. An IRE form must be completed and sent by e-mail, fax, or overnight courier to the sponsor (Please note that the IRE form is NOT the AE eCRF).

Subjects experiencing SAEs should be followed clinically until their health has returned to baseline status, or until all parameters have returned to normal or have otherwise been explained. It is expected that the investigator will provide or arrange appropriate supportive care for the subject and will provide prompt updates on the subject's status to the sponsor.

9.5 ADVERSE EVENTS OF SPECIAL INTEREST

CCI

9.6 ABUSE POTENTIAL MONITORING PLAN

A key objective of the Abuse Potential Monitoring Process (APMP) is to monitor for instances of abuse or diversion of the trial medication and other psychoactive substances. In addition to monitoring for irregularities in medication handling, AEs that may be suggestive of a developing abuse issue will also receive special attention. As part of the APMP, medication handling irregularities (MHIs) must be reported, and AEs related to abuse potential and AEs involving MHIs must be reported as Events Subject to Additional Monitoring (ESAMs) with detailed narratives.

Investigators and site staff at each trial site will be trained on reporting potentially abuse related AEs (eg, recording a description of the event in the participant's own words in the source documents as well as the eCRF, in addition to the clinical term, and to be aware that a participant's report may encompass more than one event and that these should be recorded separately). The investigators will be provided with examples of potentially abuse-related AEs, and trained on how to handle such events (eg, additional monitoring). While the investigators will be provided with examples of AE terms as a guide during trial conduct, the analysis of potentially abuse-related AEs will be based on a search of all Medical Dictionary for Regulatory Activities (MedDRA) preferred terms, all verbatim terms, and any open text fields within the AE data to identify text strings suggestive of abuse potential, in line with the 2017 FDA guidance (Assessment of Abuse Potential of Drugs).²⁹ Refer to the separate APMP documentation for complete details on MHIs and ESAMs, including documenting and reporting procedures, examples of potentially abuse related AE terms that meet the criteria for ESAM reporting, and guidance for the training of investigators and trial site staff.

